4.2.1.1.2 Maximum Intensity

Maximum overall intensity is derived from the daily intensities computed as described in Section 4.2.1.1.1 and is calculated as the maximum of the daily intensities over the period considered.

4.2.1.1.3 Presence

Presence is derived from the maximum overall intensity over the time period considered:

- None: No presence
- Grade 1, Grade 2, or Grade 3: Presence

• Missing or Unknown: Missing presence

Participants with at least one non-missing presence for a specific endpoint will be included in the analysis. Conversely, those without a non-missing presence will not be included in the analysis of the endpoint.

SAP Core Body: VAP00027

4.2.1.1.4 Time of Onset

Time of onset is derived from the daily intensities computed as described in Section 4.2.1.1.1. It corresponds to the first day with intensity of Grade 1, Grade 2, or Grade 3.

Note: If a reaction is not continuous (i.e., reaction occurs over two separate periods of time intervened by at least one daily intensity Missing or None) then the time of onset is the first day of the first occurrence.

Time of onset period is displayed as, D01-D04, D05-D09.

4.2.1.1.5 Number of Days of Occurrence During the Solicited Period

Number of days of occurrence over the period considered is derived from the daily intensities computed as described in Section 4.2.1.1.1. It corresponds to the number of days with daily intensities of Grade 1, Grade 2, or Grade 3. Number of days of presence on the solicited period with a specified intensity may also be derived.

4.2.1.1.6 Overall Number of Days of Occurrence

If a reaction is ongoing at the end of the solicited period, then the overall number of days of presence is derived from the daily intensities and the end date of the reaction after the end of the solicited period. The overall number of days of presence is:

• (End date - vaccination date) + (number of days of presence within the solicited period) - length of the solicited period + 1

If the end date is missing or incomplete (contains missing data), the overall number of days of presence will be considered as Missing.

4.2.1.1.7 Ongoing

Ongoing is derived from the last daily intensity of the solicited period computed as described in Section 4.2.1.1.1 and the maximum intensity on the ongoing period. The investigator's ongoing flag is not used because the measurement will determine the ongoing status of the reaction.

- Ongoing: if the last daily intensity of the solicited period is at least Grade 1 and the maximum intensity on the ongoing period is at least Grade 1
- Not ongoing: if the last daily intensity of the solicited period is None or the maximum intensity on the ongoing period is None.
- Missing: all other conditions (in this case, it is not included in the denominator of the ongoing analysis in the safety tables).

4.2.1.2 Unsolicited AEs

4.2.1.2.1 Presence

An observation will be considered an event if it has at least a verbatim term and is not a Grade 0 intensity event.

SAP Core Body: VAP00027

Grade 0 events are not included in safety analysis but are included in separate listings.

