development of intervention dependency or intervention abuse, new-onset diabetes or autoimmune disease, or suspected transmission of any infectious agent via an authorised medicinal product.

Note: Serious and severe are not synonymous. The term severe is often used to describe the intensity of a specific event as corresponding to Grade 3. This is not the same as serious, which is based on participant / event outcome or action criteria usually associated with events that pose a threat to a participant's life or functioning.

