4.2.1.2.2 Intensity

Intensity will be derived according to the following classification: None, Grade 1, Grade 2, Grade 3, or Missing

If the unsolicited AE is measurable and its preferred term is part of the list of solicited reactions, then the measurement is derived based upon and following the same rule of the intensity scales defined in the protocol for that measurable injection site or systemic reaction. Note the intensity could be considered as "None" (not a reaction) in the analysis despite being considered a reaction by the investigator (e.g., swelling measurement >0 mm but < 25 mm in adults)

Intensity for the other unsolicited AEs will correspond to the value reported in the CRF.

The maximum intensity corresponds to the highest intensity for a unique term.

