4.2.1.2.6 Serious Adverse Events

An event will be considered as a serious event if "Yes" is checked for "Serious" in the CRF.

SAEs will be analyzed within 28 days after vaccination, from D29 to 180 days after vaccination, and within 180 days after vaccination.

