4.2.2.6 Adverse Events Leading to Study Discontinuation

This information will be summarized as collected. A flag is available in the clinical database for all AEs in order to identify AEs leading to discontinuation before the end of active phase.

SAP Core Body: VAP00027

In general, the items that are counted are:

- Disposition table: A participant who, on the "Completion at End of Active Phase" form question "What was the participant's status?" has "Adverse Event" checked.
- Safety overview table: A participant who has either on the "Completion at End of Active Phase" form, question" What was the participant's status?" has "Adverse Event" checked or lists a solicited AE that has "Caused Study Termination" checked that is at least Grade 1 or an unsolicited AE that has "Caused Study Discontinuation" checked that is at least Grade 1 or missing and is within the time period indicated.
- System Organ Class (SOC)/Preferred Term (PT) table: A solicited AE that has "Caused Study Termination" checked that is at least Grade 1 or an unsolicited AE that has "Caused Study Discontinuation" checked that is at least Grade 1 or missing and is within the time period indicated.

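### The SAP's Grade 0 rule can take a few reported SAEs and medically attended AEs out of their rates because a measured size or temperature falls below Grade 1

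*SAP*

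**What the plan says.** SAP 4.2.1.2.1 sets the entry condition for every unsolicited AE: "An observation will be considered an event if it has at least a verbatim term and is not a Grade 0 intensity event". It continues: "Grade 0 events are not included in safety analysis but are included in separate listings".

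SAP 4.2.1.2.2 classifies intensity as None, Grade 1, 2 or 3, or Missing. It applies the protocol's measurement scale under one condition: "If the unsolicited AE is measurable and its preferred term is part of the list of solicited reactions". For such a record it accepts that the intensity may be None "in the analysis despite being considered a reaction by the investigator", with a swelling under 25 mm in an adult as its example. For everything else: "Intensity for the other unsolicited AEs will correspond to the value reported in the CRF".

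The MAAE, SAE and AESI rules (SAP 4.2.1.2.5 to 4.2.1.2.7) are subsections of the same Unsolicited AEs section. Each relies on a CRF tick, and the SAE rule opens: "An event will be considered as a serious event if". None mentions the Grade 0 rule.

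The endpoints in Protocol Table 3.1 are the occurrence of SAEs throughout the study and of MAAEs up to 28 days, with no minimum grade. Protocol 10.2.2 distinguishes serious from severe and describes seriousness as a concept "which is based on participant / event outcome or action criteria usually associated with events". Protocol 10.2.1 places SAEs within unsolicited AEs and defines an MAAE by the seeking of unplanned medical advice.

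**The concern.** Whether an event is serious or medically attended does not depend on its size in millimetres or on a thermometer reading. The SAP nevertheless makes the word 'event' conditional on derived intensity, then defines SAEs and MAAEs as kinds of event. A record the investigator has ticked Serious or MAAE can therefore fail the entry condition before the tick is considered.

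The error runs in one direction. SAP 3.4.3 keeps the denominator for unsolicited AEs at all vaccinated participants, so a dropped record lowers the numerator only. For rare outcomes, one lost record can turn one event into none observed. It also runs against the SAP's other conventions, which tend to keep doubtful events: missing causality counts as related (3.4.5.1.2) and missing onset is included in the 28-day tables (4.2.1.2.3). SAP section 5 does not list this exclusion among the changes.

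**Working it through.** The documents give no figure for this rule, so there is none to reproduce. The check has three parts.

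**1. What Grade 0 means.** The SAP does not define it. Of the five intensity categories in 4.2.1.2.2, None is the only one that can correspond to it. SAP 4.2.2.6 supports this: a flagged unsolicited AE counts there if it has the discontinuation box "checked that is at least Grade 1 or missing and is within the time period indicated", which keeps every category except None. Reading Grade 0 as None is an inference, but a well-supported one. Missing intensity stays missing (SAP 3.4.5.1.3) and is not Grade 0.

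**2. Which records can derive to None.** The scales in Protocol Tables 10.1 to 10.3 were applied to test readings of 20 mm and 37.8°C:

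| Age | Erythema | Swelling | Induration | Bruising | Fever term |
|---|---|---|---|---|---|
| 10 | Grade 1 | Grade 1 | Grade 1 | Grade 1 | None |
| 14 | None | None | Grade 1 | Grade 1 | None |
| 30 | None | None | Grade 1 | Grade 1 | None |

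Erythema and swelling start at Grade 1 from 25 mm at age 12 and over, but from any size above 0 mm at ages 2 to 11. Induration and bruising are graded from above 0 mm at all ages. Fever starts at 38.0°C at all ages. The measurement route can therefore remove only:

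- injection-site erythema or swelling above 0 but under 25 mm at age 12 or over;
- a fever term with a reading below 38.0°C, at any age.

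The SAP's example mentions adults, but the protocol threshold applies from age 12. Within the 9 to 17 group, a 20 mm swelling is kept at age 10 and dropped at age 14.

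These terms are normally unsolicited only if they start after the D01 to D08 solicited window (Protocol 8.3.1 and 10.2.1). The realistic case is a late-onset small reaction or low temperature for which the participant sought medical advice.

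**3. Effect on a rate.** Take n = 667 vaccinated per age group, the planned enrolment, and assume 0 to 3 participants in the numerator, since the documents give no count. The rate is x/n. The exact (Clopper-Pearson) limits are the 2.5% quantile of Beta(x, n − x + 1), set to 0 when x = 0, and the 97.5% quantile of Beta(x + 1, n − x).

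| x | Rate = x/667 | 95% CI |
|---|---|---|
| 0 | 0.00% | 0.00 to 0.55% |
| 1 | 0.15% | 0.00 to 0.83% |
| 2 | 0.30% | 0.04 to 1.08% |
| 3 | 0.45% | 0.09 to 1.31% |

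Each participant lost takes 1/667 = 0.15 percentage points from the group rate, or 1/1334 = 0.075 points overall. These figures show what one lost participant does; they do not estimate how many would be lost.

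**The case against.** The strongest reply is that the affected set is close to empty. Protocol 10.2.3 asks for the diagnosis rather than the sign to be recorded where possible, so a hospital admission would usually be entered under a diagnosis graded from the CRF, not as a temperature under 38.0°C. MAAEs exclude solicited reactions by definition. Dropped records remain in separate listings, and SAEs reach the sponsor within 24 hours whatever the tables show. The thresholds and their use for measurable unsolicited AEs come from the protocol itself (10.2.5.1.2), and Protocol section 9 leaves analysis conventions to the SAP.

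Much of this stands. It makes a dropped SAE very unlikely and confines the practical issue to late-onset MAAEs. It does not remove the gap. Protocol 10.2.5.1.2 says how to grade these events, not that an event below Grade 1 ceases to be one; the exclusion is the SAP's own. A listing does not restore a participant to a rate or its interval.

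A reader might also infer three stronger points that the documents do not support:

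- **AESIs are dropped too.** No AESI listed in Protocol 8.3.6 is a measurable solicited term. Their intensity comes from the CRF, so this route cannot remove a listed AESI.
- **Discontinuation rates are lowered in the same way.** Under SAP 4.2.2.6 the disposition table counts a participant whose completion form gives Adverse Event, and the overview table accepts that tick as an alternative to a graded AE. Neither puts a grade condition on the tick. The filter acts mainly on the SOC/PT table, which could then disagree with the overview.
- **The events disappear.** They leave the summary tables, not the listings.

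**Conclusion.** The point holds in a narrow form. As written, the SAP excludes from the SAE and MAAE rates a ticked unsolicited record whose preferred term is a measurable solicited term and whose measurement is below Grade 1. That conflicts with protocol endpoints that carry no intensity floor and with the protocol's separation of seriousness from intensity.

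The conclusion rests on two readings: that Grade 0 means None, and that the SAE and MAAE rules, placed under the Unsolicited AEs heading and worded in terms of an event, inherit that section's entry condition. Neither is stated outright; both follow from the text.

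The size is unknown and probably very small. It is a minor point, worth correcting because a programmer following the text exactly would leave a reported event out of an endpoint rate.

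**What to change.** In SAP 4.2.1.2.1, define Grade 0 (for example, as a derived intensity of None under 4.2.1.2.2) and add: *The Grade 0 exclusion does not apply to events ticked Serious or MAAE; these are counted in their tables with intensity shown as below Grade 1.*

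In SAP 4.2.2.6, align the unsolicited-AE grade condition of the SOC/PT table with the overview table. A participant counted in the overview through the completion form should then have the responsible unsolicited AE shown even if its derived grade is None.

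The main change costs one sentence and one programming condition, plus the definition and the alignment in 4.2.2.6. The only drawback is that a few events may appear without a grade of 1 to 3. If the sponsor already means to count these events, the sentence simply records that.

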4.2.1.2.2 Intensity

Intensity will be derived according to the following classification: None, Grade 1, Grade 2, Grade 3, or Missing

If the unsolicited AE is measurable and its preferred term is part of the list of solicited reactions, then the measurement is derived based upon and following the same rule of the intensity scales defined in the protocol for that measurable injection site or systemic reaction. Note the intensity could be considered as "None" (not a reaction) in the analysis despite being considered a reaction by the investigator (e.g., swelling measurement >0 mm but < 25 mm in adults)

Intensity for the other unsolicited AEs will correspond to the value reported in the CRF.

The maximum intensity corresponds to the highest intensity for a unique term.

4.2.1.2.3 Time of Onset

Time of onset is derived from the start date of the unsolicited AE and the date of vaccination:

Time of Onset = start date of the unsolicited AE - date of vaccination + 1 (if D01 is the first vaccination day).

The time of onset is considered as missing only if one or both dates are missing or partially missing.

The unsolicited AEs will be analyzed "Within 28 days" after vaccination, which corresponds to AEs with a time of onset between D01 and D29 or missing. An AE with missing time of onset will be considered to have occurred just after the vaccination, so will be included in these tables.

Time of onset period is displayed as D01-D04, D05-D08, D09-D15, D16 or later, and Missing.

Note: Unsolicited AE that occurred before vaccination (negative time of onset) or with a time of onset higher than defined above will not be included in analysis but will be listed separately.

4.2.1.2.4 **Duration**

Duration is derived from the start and end dates of the unsolicited AE:

• Duration = End date of unsolicited AE - start date of unsolicited AE + 1.

The duration is considered as missing only if one or both of the start and end dates of the unsolicited AE is missing or partially missing.

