3.4.5.1.4 Start Date and End Date

Missing or partially missing start dates or end dates for unsolicited AEs (including SAEs) will remain missing and not be imputed. If the start date is missing or partially missing, the time of onset will be considered missing. If either the start date or end date is missing or partially missing, the duration will be considered missing.

SAP Core Body: VAP00027

Missing or partially missing end dates for ongoing solicited AEs will remain missing and not be imputed.

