4.2.1.2.7 Adverse Events of Special Interest

An event will be considered as an AESI if "Yes' is checked for "Is the event an AESI?" in the CRF.

AESIs will be analyzed within 28 days after vaccination, from D29 to 180 days after vaccination, and within 180 days after vaccination.

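### The SAP counts an unsolicited event with a partly missing start date as within 28 days even when its known month falls after D29, and D29 lies in both safety periods

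*SAP*

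**What the plan says.** **Partial dates.** SAP 3.4.5.1.4 reads: "Missing or partially missing start dates or end dates for unsolicited AEs (including SAEs) will remain missing and not be imputed". It adds: "If the start date is missing or partially missing, the time of onset will be considered missing". SAP 4.2.1.2.3 agrees: "The time of onset is considered as missing only if one or both dates are missing or partially missing".

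**Early period.** SAP 4.2.1.2.3 says that the within-28-days analysis "corresponds to AEs with a time of onset between D01 and D29 or missing", and on missing onset: "An AE with missing time of onset will be considered to have occurred just after the vaccination, so will be included in these tables". A note in the same section removes events before vaccination, or with onset beyond that range, from the analysis and lists them separately. The onset display has its own Missing row. SAP 3.5 also equates within 28 days with D01 to D29.

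**SAE and AESI periods.** SAP 4.2.1.2.6: "SAEs will be analyzed within 28 days after vaccination, from D29 to 180 days after vaccination, and within 180 days after vaccination". SAP 4.2.1.2.7: "AESIs will be analyzed within 28 days after vaccination, from D29 to 180 days after vaccination, and within 180 days after vaccination". SAP 4.2.1.2.5 sets the same three periods for MAAEs. None of these sections has a rule for missing onset.

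**Collection.** Protocol 8.3.1 collects non-serious unsolicited AEs and MAAEs to D29, and SAEs and AESIs to D181. Protocol 10.2.1 counts SAEs among unsolicited AEs.

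**The concern.** Two date rules can place an event in the wrong period.

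- **Partial dates.** The SAP intends events with onset outside D01 to D29 to leave the within-28-days analysis. A missing day switches that exclusion off, even when the recorded month shows that the event started later.
- **Overlapping periods.** The early and late periods share D29, so their counts need not add up to the 180-day count.

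SAEs and AESIs are listed safety endpoints. Readers use the early and late split to judge timing relative to vaccination. With few events, one in the wrong column is visible.

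**Working it through.** **1. Day numbering.** SAP 4.2.1.2.3 gives: "Time of Onset = start date of the unsolicited AE - date of vaccination + 1".
- 28 days after vaccination: 28 + 1 = D29. This reproduces the SAP's D01 to D29.
- 180 days after vaccination: 180 + 1 = D181, the end of SAE collection in Protocol 8.3.1.

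**2. Do the periods partition the follow-up?**

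| Late period starts | Early days | Late days | Sum | Whole period | Shared |
|---|---|---|---|---|---|
| D29 (as written) | 29 | 181 − 29 + 1 = 153 | 182 | 181 | D29 |
| D30 (proposed) | 29 | 181 − 30 + 1 = 152 | 181 | 181 | none |

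The early count is the same in both rows. Only the late count gains a day. If SAE onsets were uniform over D01 to D181 (assumption), D29 would hold 1/181 = 0.55% of SAEs, and the late count would be inflated by 153/152 − 1 = 0.7%.

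**3. Partial-date example (dates assumed).** Vaccination on 15 November 2022 is D01, so D29 is 13 December 2022. An SAE is dated March 2023, day unknown.
- 1 March 2023 is 15 + 31 + 31 + 28 + 1 = 106 days later, which is D107.
- 31 March 2023 is 30 days after that, which is D137.

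The event lies between D107 and D137, at least 107 − 29 = 78 days past the early period. Under 4.2.1.2.3 its onset is missing and it counts as within 28 days.

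**4. Would the known month usually settle the matter?** For assumed vaccination dates from November 2022 to late April 2023, the calendar month lies wholly after D29 for 80% to 100% of the late days D30 to D181 (mean about 90%). A month that straddles D29 does not settle it. In the example, December 2022 runs from D17 (16 days after vaccination, plus 1) to D47 (46 + 1) and is compatible with the early period.

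**5. Size, if the rule is carried to SAEs.** The documents give neither an SAE rate nor a number of partial dates. Assume 20 SAEs with uniform onset: the true early count is 20 × 29/181 = 3.2 and the true late count is 20 × 152/181 = 16.8. Let q be the share with a partial date.
- Reported early = 3.2 + q × 16.8.
- Reported late, if those events also leave the late period (not stated in the SAP) and D29 is counted there = (1 − q) × (16.8 + 20/181).

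| q (assumed) | Reported early | Reported late |
|---|---|---|
| 0% | 3.2 | 16.9 |
| 5% | 4.0 | 16.1 |
| 10% | 4.9 | 15.2 |

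For a single event, the group rate moves by 1/667 = 0.15 percentage points. If the true early count in a group is 1 to 3 (assumption), one extra event raises it by 33% to 100%.

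**6. MAAEs.** Collection ends at D29 (Protocol 8.3.1), while SAP 4.2.1.2.5 plans a table from D29 to 180 days. The only day of that table inside the collection period is D29, which the early table already counts.

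**The case against.** **The missing-onset rule may not govern SAEs.** It refers to the unsolicited-AE tables, and 4.2.1.2.6 and 4.2.1.2.7 set their own periods. Section 4.2.1.2.3 also cannot be carried over whole: its note would drop every SAE after D29, against 4.2.1.2.6. This stands, so the SAE and AESI part of the point is conditional. A reader might infer that the SAP orders late SAEs to be removed from the late period, but no text says so. The link to SAEs rests on reading 3.4.5.1.4, 4.2.1.2.3 and Protocol 10.2.1 together. What remains is that the SAE and AESI sections are silent.

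**Partial dates should be rare for SAEs.** A reader might suppose that recall at the 6-month call makes them common. The documents do not support that. SAEs are reported within 24 hours (Protocol 8.3.1), the investigator reviews the medical documentation (Protocol 10.2.3), and a memory aid is reviewed at the call with unclear items clarified (Protocol 1.3). Non-serious AEs are collected only to D29, so for them the rule can seldom misplace an event. This stands and limits the size.

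**Events before vaccination.** The rule would in form also admit an event whose known month precedes vaccination. Consent, blood sampling and vaccination share Visit 1, and before vaccination only procedure-related SAEs are collected, so almost no such event can arise.

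**Counting unknown onset as early is conservative.** It matches the SAP's treatment of missing causality as related (3.4.5.1.2). That is reasonable for a wholly unknown date or one compatible with D01 to D29. It is not reasonable when the recorded month contradicts it. The Missing row makes such events visible in the onset display, but they stay in the 28-day total.

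**Conclusion.** The point holds as a minor correction.

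- **Certain from the text:** a partly missing start date puts an unsolicited event in the within-28-days count whatever its known month, and D29 belongs to both periods.
- **Conditional:** a late SAE or AESI with an unknown day is tabulated as early only if the 4.2.1.2.3 definition is used in those tables. The SAP does not say whether it is, nor whether such an event would also appear in the late period.

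A reader might infer that both defects distort both periods. They do not: the overlap adds only to the late count (about 0.7% under uniform onset), and the early count is affected only by partial dates. The larger relative figures rest on assumed event counts and assumed shares of partial dates, and the real number of partial dates is unknown. The 180-day total is unaffected, safety is descriptive without hypothesis tests, and the primary objective is untouched.

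**What to change.** 1. **SAP 4.2.1.2.3, with 3.4.5.1.4 aligned:** count a partial start date within 28 days only if its known part is compatible with D01 to D29. Otherwise allocate the event to the period that the known month and year imply. Keep wholly unknown dates in the early period, as now.
2. **SAP 4.2.1.2.6 and 4.2.1.2.7:** state that this rule applies to the SAE and AESI period tables, so that each event falls in one sub-period.
3. **SAP 4.2.1.2.5 to 4.2.1.2.7:** start the second period at D30.
4. **SAP 4.2.1.2.5:** reconcile the MAAE late period with MAAE collection that ends at D29 in Protocol 8.3.1.

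The cost is a few lines of SAP text and programming. No new data are needed.
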